Baseline labs including a comprehensive metabolic panel, lipid panel, and hemoglobin A1C will be assessed (unless labs within 3 months are available). Additional blood will be stored for future biomarker analysis. These blood samples will be stored in the Research commons freezer or the Winters Center freezers located in building 110 at the MEDVAMC. The biomarker analyses to be performed will be based on additional funding that will be obtained as the current grant that supports this study will not have adequate funds to run additional biomarkers. Hence while related to the study in that all the data from this study will be used, the funding is to be obtained in the future and the biomarkers to be decided in the future. Blood from only those who meet the troponin inclusion criteria and who are ultimately randomized to this study will be stored. The others will be discarded.

Randomization visit and titration of medications: After the pre-randomization visit, those individuals who meet the inclusion criteria including hs-cTnT levels, HF risk score will come for the randomization visit. A history (medical, surgical, social, family and medication history and review of systems) and physical examination will be performed, and the findings will be documented on the case report form. The physical examination

would include BP measurements (3 taken 2 minutes apart). Orthostatic BP measurements will be performed as well. We will use calibrated BP machines in the clinic for the purpose of the study. They will have a 2D and 3D echocardiogram with Doppler. Those with adequate images for cardiac strain assessment will then be randomized to one of the 3 groups. Randomization will be achieved with the help of the research pharmacy and ICTR (institute for clinical and translational research). Randomization will be stratified for age, presence of CHD, ACE-inhibitor/ARB use, and hs-cTnT levels greater than 14 ng/L. In addition to an echocardiogram, a carotid ultrasound and a pulse wave velocity assessment will be performed at the randomization visit

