Subjects randomized to the spironolactone group will be started at 25 mg daily, and titration up to 50 mg daily will be attempted (blood pressure, potassium levels permitting). Briefly, subjects will start taking their medication and 2 weeks later return for a brief visit when BP and potassium will be checked. If BP is greater than 125 mm Hg, spironolactone will be increased to 50 mg daily. Once maximum dose is achieved, serum potassium will be measured to ensure stability. For those randomized to spironolactone who have eGFR between 50 and 60 ml, medication will be started at 12.5 to 25 mg daily and then potassium, renal function measured at 2 weeks and 6 weeks and medication titrated based on results. In addition for those subjects with blood pressure on the lower side (120-130 mmHg systolic) or per principal investigators discretion spironolactone may be started at 12.5 mg daily for the first few days to ensure safety/ tolerability and then increased to 25 mg daily.

Subjects in the carvedilol group will similarly be started at 6.25 mg PO 2 times daily and titrated up to a maximum dose of 25 mg PO 2 times daily, again monitoring BP. Titration will be continued provided the systolic BP is >125 mm Hg. In addition for those subjects with blood pressure on the lower side (120-130 mmHg systolic) or per principal investigators discretion carvedilol may be started at 3.25 mg two times daily for the first few days to ensure safety/ tolerability and then increased to 6.25 mg two times daily.

Subjects in the usual-care group will continue receiving treatment from their primary care physician. However they will be required to come to the research clinics at baseline, 6 months, 12 months and at the end of study when history, physical, blood biomarker collection and imaging will be done similar to the carvedilol/ spironolactone treatment groups.

Visit 2: Subjects randomized to the spironolactone or carvedilol groups will come back for a 2-week visit, when they will have their BP checked and medications titrated if required. Those in the spironolactone arm will also have their serum potassium measured. As noted above for those on spironolactone and eGFR between 50-60 ml, potassium and renal function will be repeated at 6 weeks as well. Subjects may be called by the research coordinators approximately every 8 weeks for the first 6 months to enquire about tolerability and compliance. In addition this may help with subject retention.

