Visit 3: All subjects will return at 6 months. During the 6-month visit, all subjects will have a history and physical examination completed, and blood will be collected and part stored. Additionally, subjects will be interviewed about clinical events, including hospitalization, during the 6-month interval. Medication compliance will be assessed at this visit. Those on spironolactone will have their potassium checked

Visit 4: The 12 month visit will be identical to the 6 month visit

Visit 5: The final visit will capture details as in visit 3 and 4 but in addition also include all the imaging studies (echocardiogram, carotid ultrasound and pulse wave velocity measurement). Blood will be collected as well for biomarker assessment and additional samples stored for future research.

Subjects will be encouraged and requested to call/ notify us about any adverse events including side effects to medication, hospitalization, emergency room or urgent care visits. If there are any hospitalizations/ emergency room/ urgent care visits we will obtain information from the VA electronic medical record or from the hospital/ emergency room where they were cared for. There will be both paper and electronic data that will be nearly similar. The paper data will include the following HIPPA identifiers: name, date of birth, age, last four of the social security number, date of hospital admissions, date of discharge and any date of clinic visit during the duration of the study as well as participant address, phone number and email ID (if available). The electronic data stored at the VA will include name, last 4 of the social security number, date of birth, date of hospital admissions, date of discharge, any date of clinic visit and the research ID during the duration of the study. Electronic data stored in the BCM database which will be used for analysis will not have any HIPAA identifier and will include all other information. Data will be stored such that date of consent will be called "Day 0" and then other study events will be time stamped relative to the date of consent (example 6 month visit will be day 180 and so on). A date of birth will not be noted, but subject age will be recorded as this will be important in data analysis.

Sample Size/Data Analysis

Sample Size

How many subjects (or specimens, or charts) will be used in this study?

Local: 850 Worldwide: 850

Please indicate why you chose the sample size proposed:

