Secondary Analysis: For each of the primary and secondary end points, the longitudinal mixed-effect model will be applied to compare the slope differences among the usual care and two drug treatment groups with and without adjusting baseline covariates. The main model can be described as mean outcome at time $t = b_0 + b_1*t + b_2*group + b_3*t*group$. The within-subject correlation structure will be assumed to follow spatial power correlation structure because of its uneven observational time intervals. The generalized estimation equation method will be used to perform the analysis. Secondary, exploratory analyses will be performed to evaluate prespecified subgroups; we will test changes in cardiac and carotid strain in responders (e.g., those whose cTnT levels stayed stable or decreased, those whose hs-cTnT levels were greater than 14 ng/L at baseline, those whose estimated HF risk was greater than 10%) in comparison with nonresponders.

Potential Risks/Discomforts

Potential Risks/Discomforts

Describe and assess any potential risks/discomforts; (physical, psychological, social, legal, or other) and assess the likelihood and seriousness of such risks:

1. Medications: Carvedilol and spironolactone are clinically used, generally well tolerated with limited side effects. Both medications lower blood pressure which will be closely monitored. Spironolactone can lead to hyperkalemia (increased potassium levels) and at higher doses can cause gynecomastia (mostly reversible). However we are excluding individuals with renal insufficiency and using lower dose spironolactone which will decrease the risk of these occurrences. Furthermore for those on spironolactone we will check their potassium levels after starting the medication and during each study visit. With carvedilol other than lower blood pressures and possibly a slower heart rate no other significant side effects are anticipated. Idiosyncratic reactions such as allergies to medications etc. are possible

2. As with any clinical study despite our best efforts, loss of confidentiality is possible

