3. The imaging tests are predominantly clinically used ultrasound based and have negligible side effects. Heating of tissue is a possibility with ultrasound imaging but we will not exceed the industry recommended standards. Subjects will be lying down when the studies are done and given that we will require approximately 40-45 minutes to complete the studies physical discomfort from lying down is possible in some of the subjects. The arterial stiffness measurement (pulse wave velocity) just involves tracking the pulse with a hand held tonometer in the arm and the groin (femoral artery) and has no known side effects other than momentary discomfort
4. Some individuals may be allergic to the stickers used to connect ECG leads and if placed in a hairy area of the chest may result in some pain when removing them
5. Given this is a study that will include individuals greater than 40 years of age, women of child bearing potential will be eligible for recruitment. Any woman who has child bearing potential and is interested in participating in the study will need to undergo a pregnancy test (urine) and only if negative will be eligible for the study. Furthermore, we will discuss and require that they have a contraception plan in place in order to participate
6. Finally with blood draws the usual possibilities including feeling faint/ fainting/ infection and pain exist but not any more than that which will happen during routine clinical care

Safety measures: The study drug will be discontinued in subjects with any allergic reaction to the study drugs or side effects from these drugs. In subjects receiving spironolactone, serum potassium will be monitored prior to each dose change and within 7 to 14 days after a dose change. Potassium supplements will be stopped before the start of spironolactone and will be allowed only if the serum potassium is less than 4.0 mEq/L after the study drug is started.

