The spironolactone dosage will be adjusted based on the following algorithm which has been used in other clinical studies: if serum potassium is greater than or equal to 5.0 mEq/L but less than 5.5 mEq/L, the dose will not be increased; if serum potassium is greater than or equal 5.5 but less than 6.0 mEq/L, the dose will be reduced by half; if serum potassium is greater than or equal to 6.0 mEq/L, spironolactone will be stopped but could be restarted at the lowest dose if a correctable underlying condition for hyperkalemia is readily identified and serum potassium is reduced to less than 5.0 mEq L. For those individuals with eGFR between 50 and 60 ml, an additional lab test will be done at 6 weeks to follow up on renal function and potassium For subjects receiving carvedilol, any symptomatic bradycardia or atrioventricular blocks greater than first degree will result in stopping the medication. Additionally, any symptom of low BP (e.g., dizziness) that is bothersome to the subject will result in stopping the medication. A data safety monitoring board has been assembled (VA hospital, Chicago) and will oversee the study safety.

Data and safety monitoring plan

Do the study activities impart greater than minimal risk to subjects?

Yes

NOTE: The answer to the questions in H2 requires the completion of the form: 'Section H – Data and Safety Monitoring Plan' as an attachment in Section S.

H3. Coordination of information among sites for multi-site research

Is the BCM Principal Investigator acting as the SPONSOR-INVESTIGATOR for this multi-site research?

No or Not Applicable

Is BCM the COORDINATING CENTER for this multi-site research?

No or Not Applicable

Potential Benefits

Describe potential benefit(s) to be gained by the individual subject as a result of participating in the planned work.

There are NO direct benefits to the subject that are anticipated.

Describe potential benefit(s) to society of the planned work.

Cardiac troponin T has been identified as an excellent marker of incident cardiovascular disease including heart failure. Currently there is no known therapeutic strategy in which asymptomatic individuals with elevated troponin T. Our strategy aims to test 2 anti-hypertensive medications at blood pressure ranges where treatment is not pursued usually. If positive this study may in the future help identify a strategy that could be valuable in the prevention of incident CHF

Do anticipated benefits outweigh potential risks?

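### Carvedilol may be raised on systolic BP alone: no heart-rate condition is written into the titration rule, and no pulse is listed at the titration visit

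*Combined protocol and SAP*

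**What the plan says.** Under Randomization visit and titration of medications, carvedilol starts at 6.25 mg twice daily and goes up to at most 25 mg twice daily with BP monitored. A lower start is optional when BP is on the low side or at the investigator's discretion. The condition for going on is "Titration will be continued provided the systolic BP is >125 mm Hg".

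Visit 2, at two weeks, brings both drug arms back, "when they will have their BP checked and medications titrated if required". Potassium is added there for the spironolactone arm; nothing is added for carvedilol.

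Under Potential Risks/Discomforts, item 1, the plan states: "With carvedilol other than lower blood pressures and possibly a slower heart rate no other significant side effects are anticipated". The Safety measures in the same section say that for carvedilol "any symptomatic bradycardia or atrioventricular blocks greater than first degree will result in stopping the medication". They also stop it for bothersome symptoms of low BP.

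For spironolactone, the Procedure section says "titration up to 50 mg daily will be attempted (blood pressure, potassium levels permitting". The Safety measures require potassium before each dose change and again 7 to 14 days after it, and give potassium bands at which the dose is held, halved or stopped.

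**The concern.** The plan recognises that carvedilol may slow the heart, but heart rate plays no part in the decision to give more of it. The rate-based stopping rule acts only once there are symptoms. Between a normal pulse and symptomatic bradycardia lies a range in which a careful prescriber would normally pause, and the written rule is silent on it.

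What is at stake is participant safety. The protocol classes the study as more than minimal risk with no prospect of direct benefit, and its risk-benefit discussion concedes that drug is started at pressures where treatment is not usually recommended. In that setting a simple pulse condition before raising a beta-blocker is a reasonable expectation.

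**Working it through.** No figure in the plan bears on this point, so the check is mainly a comparison of texts.

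**The two drugs side by side**

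| Element | Spironolactone | Carvedilol |
|---|---|---|
| Drug-specific effect named in the risk section | Raised potassium | Possibly a slower heart rate |
| Listed at Visit 2 | BP and potassium | BP |
| Marker check tied to each dose change | Yes, before and 7 to 14 days after | None written |
| Hold rule | Potassium 5.0 to below 5.5 mEq/L | None on heart rate |
| Reduce rule | 5.5 to below 6.0 mEq/L: halve | None on heart rate |
| Stop rule | 6.0 mEq/L or above | Symptomatic bradycardia, or AV block beyond first degree |

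**Applying the rule as written.** Take a subject with systolic BP of 130 mm Hg, a resting pulse below 50 and no symptoms. The BP condition is met (130 > 125). The bradycardia stop is not met, because it needs symptoms. Nothing in the titration text bars the next dose, and nothing in it requires the pulse to have been taken.

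**Opportunities to notice**
- In-person contacts from randomisation on: the randomisation visit plus Visits 2, 3, 4 and 5 = 5.
- With a physical examination listed: randomisation and months 6, 12 and 18 = 4. At Visit 3, for example, "all subjects will have a history and physical examination completed". Without one: Visit 2 = 1.
- Visit 2 to Visit 3: the protocol's example puts the 6-month visit at day 180. 180 − 14 = 166 days, and 166/7 = 23.7, about 24 weeks. This is approximate, because the protocol counts days from consent.
- Optional calls every 8 weeks over about 26 weeks: 26/8 = 3.25, about 3. They ask about tolerability and compliance.

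**Number of increases.** 25/6.25 = 4. If each step doubles the dose (an assumption; step size is not stated), log2(4) = 2 increases are needed; if the dose goes directly to the maximum, 1. With doubling, no in-person visit is scheduled for the second increase. The BP condition still implies that someone obtains a BP reading then, so an unscheduled titration contact must occur.

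**Subjects under the rule.** The sample-size justification gives 205 to 210 subjects in three equal groups: 205/3 = 68.3 and 210/3 = 70.

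**The case against.** The strongest reply is that the BP sentence permits titration and does not command it. Visit 2 adjusts medication only where required, and the stopping rules override any increase. That is right. A reader might infer that the protocol orders escalation in a subject with a slow pulse. It does not; the accurate statement is that such a subject is not barred.

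There is also real protection elsewhere. At entry, current atrial fibrillation and other beta-blocker use are excluded, the investigator may exclude anyone thought to be at risk, and history, examination and echocardiogram come first. On treatment, there are adverse-event reporting, a safety board and a general rule: "The study drug will be discontinued in subjects with any allergic reaction to the study drugs or side effects from these drugs". Read literally with the risk section, which lists a slower heart rate among side effects, that rule might even cover a symptomless slow pulse. But the carvedilol-specific rule asks for symptoms, so the two readings differ, and neither provides for a pulse to be taken before a dose increase.

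The contrast with spironolactone should not be pushed too far. Its operative step in the Procedure section is also triggered by BP above 125 mm Hg; the holding rule sits in the Safety measures. What stands is that the Safety measures contain a pre-dose check and a hold rule for one drug and not for the other.

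In practice staff or the BP machine may well record pulse. The text neither says so nor links it to dosing. Finally, the Data and Safety Monitoring Plan is a separate attachment that was not available, so absence of a check from the whole plan is not proven.

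**Conclusion.** The point holds as a gap in a stated dosing rule: within the available text, carvedilol increases depend on systolic BP and not on heart rate, and the main titration visit lists no pulse. It is a modest safety matter and a cheap improvement.

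The 68 to 70 subjects are those governed by the rule, not those at risk. The documents give no frequency of bradycardia or block, so no number affected can be derived.

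Three stronger readings are tempting and are not supported:
- That the plan expects bradycardia. It says only that slowing is possible.
- That a pulse check would also find symptomless AV block. A pulse count cannot do that reliably, so the remedy should not be sold on it.
- That the primary or secondary endpoints are affected. Nothing in the documents shows this, and it is not claimed.

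Nor is a new exclusion criterion needed: it would not address a slow, symptomless pulse arising on treatment, and it would overlap the existing investigator-opinion exclusion. The conclusion assumes that the unavailable monitoring plan contains no such check.

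**What to change.** 1. Record resting pulse alongside BP at Visit 2 and at every titration contact, scheduled or not.
2. Reword the carvedilol condition along these lines: carvedilol is increased only if systolic BP is above 125 mm Hg, resting heart rate is at or above a limit fixed in advance by the investigators, and no carvedilol stopping condition in the Safety measures is known to be present.
3. Choose that limit before the rule is used. The documents give none; 50 to 60 bpm is an assumed range to choose within.
4. If the Data and Safety Monitoring Plan already contains the check, cite it in the titration text and add nothing further.

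The cost is one sentence and a pulse count at contacts where BP is already being taken. The downside is that some carvedilol subjects will stay at a lower dose, and a limit of 60 bpm would hold back more of them than one of 50 bpm.

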Data on change in strain with various medications are limited. However, a 1 to 1.5% absolute difference in longitudinal strain has been associated with outcomes. Therefore, assuming a conservative standard deviation of 3% (as described in studies), an alpha of 0.05, and a power of 0.8, we would require approximately 62 subjects per group.

Therefore, a sample size of 205-210 subjects should be a reasonable estimate (accounting for an approximately 10% drop-out rate)

Data Analysis

Provide a description of your plan for data analysis. State the types of comparisons you plan (e.g. comparison of means, comparison of proportions, regressions, analysis of variance).

Which is the PRIMARY comparison/analysis? How will the analyses proposed relate to the primary purposes of your study?

Primary analysis: To better inform the analyses planned, descriptive statistics (means and standard deviations of continuous variables and frequency of discrete variables) of subjects demographic characteristics and echocardiogram, vascular ultrasound, and biomarker variables will be computed at each measurement time and compared among the usual care and two drug treatment groups. All analyses will be conducted using the intention-to treat(ITT) principle. Statistical tests with a 2-sided P-value less than 0.05 will be considered statistically significant. When multiple comparisons are involved, Bonferroni correction for the type I error will be applied. Each continuous primary and secondary outcome will first be examined for its normality using the Shapiro Wilk test. When normality is verified, an analysis of variance (ANOVA) approach will be used to compare the mean change among the usual care and two drug treatment groups. Pairwise comparisons between the usual care and each of the drug groups will also be performed using the least significant difference method under the ANOVA framework. When the normality assumption is violated, the Kruskal Wallis nonparametric test will be applied.

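### The trial is sized at uncorrected alpha 0.05, but Bonferroni and LSD are not reconciled for the two drug-versus-usual-care tests: per-drug power at 1.5% is about 70% under Bonferroni, and ungated LSD has about 9% family-wise error

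*Combined protocol and SAP*

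**What the plan says.** All the relevant text is in the combined protocol and SAP, under Sample Size/Data Analysis.

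**Sample Size.** The justification begins by noting that "Data on change in strain with various medications are limited" and that "a 1 to 1.5% absolute difference in longitudinal strain has been associated with outcomes". It goes on, "assuming a conservative standard deviation of 3% (as described in studies", to the result: "an alpha of 0.05, and a power of 0.8, we would require approximately 62 subjects per group". With about 10% drop-out the total is 205-210. The section does not say which difference in the range was used, or whether 3% is the SD of one measurement or of the change.

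**Data Analysis, primary analysis.** Significance is a two-sided P below 0.05. Then:

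- On multiplicity: "When multiple comparisons are involved, Bonferroni correction for the type I error will be applied"
- When normality holds, "an analysis of variance (ANOVA) approach will be used to compare the mean change among the usual care and two drug treatment groups"
- For the two drug contrasts, placed within that ANOVA: "Pairwise comparisons between the usual care and each of the drug groups will also be performed using the least significant difference method"
- For data that fail the normality check: "When the normality assumption is violated, the Kruskal Wallis nonparametric test will be applied"

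The Bonferroni family is not defined. The pairwise tests are not made conditional on the F-test. No pairwise test is named after Kruskal-Wallis.

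**Purpose and Objectives** compares treatment with usual care and names the two drugs as alternatives. **Design** names cardiac strain as the primary end point.

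**The concern.** LSD makes no adjustment for each comparison, and Bonferroni does. Two analysts could each follow this section faithfully and test the same two contrasts at different thresholds: 0.05 for one, 0.025 for the other.

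Each possible rule leaves something unmet. Bonferroni controls the error rate, but the sample size was not worked out at the corrected alpha. Ungated LSD matches the alpha used for the sample size, but it does not hold the family-wise error at 5%. F-gated LSD controls the error, but the gate is not written and its power is not the stated 0.8.

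The two contrasts with usual care show which drug, if either, improves strain, and the F-test cannot do that. If the rule is still open once strain results by group are known, the choice can decide whether a drug is called effective.

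**Working it through.** **Inputs.** From the Sample Size section: difference 1 to 1.5%, SD 3%, alpha 0.05, power 0.8, 62 per group, drop-out about 10%. From Data Analysis: two-sided tests, change compared across three groups, two contrasts with usual care. From Design: equal allocation. Assumption for steps 1 to 4: 3% is the SD of the change.

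**1. The plan's own figure.** n per group = 2(z₁₋α/₂ + z₀.₈)² SD²/d².

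- d = 1.5, alpha 0.05: 2(1.960 + 0.842)² × 9/2.25 = 62.8
- d = 1.0, alpha 0.05: 141.3
- d = 1.5, alpha 0.025: 76.0
- d = 1.0, alpha 0.025: 171.1

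Of these, only 1.5% with uncorrected alpha gives about 62. The total follows: 3 × 62 = 186, and 186/0.9 = 207. The arithmetic is sound.

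**2. Power per comparison at 62 per group.** The noncentrality is d/(3√(2/62)) = d/0.539, which is 2.78 at 1.5% and 1.86 at 1.0%. With the pooled-variance t on 183 df:

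| Difference | alpha 0.05 | alpha 0.025 |
|---|---|---|
| 1.5% | 79.1% | 70.0% |
| 1.0% | 45.5% | 34.5% |

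The difference detectable with 80% power is 1.52% uncorrected and 1.67% under Bonferroni. For Bonferroni to reach 80% per drug at 1.5%, the SD of the change must be about 3 × 1.5/1.67 = 2.69 or less.

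**3. Three-group F-test.** λ = 62 Σ(μᵢ − μ̄)²/9, on 2 and 183 df. If both drugs give 1.5%, or one does and the other is inert, λ = 62 × 1.5/9 = 10.3 and power is 82%. If the second drug has half the effect, λ = 62 × 1.125/9 = 7.75 and power is 70%.

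**4. The three possible rules.** Simulation of 2,000,000 trials per case, with 62 per group, SD 3% and pooled variance. Bonferroni tests each contrast at 0.025. Gated LSD tests at 0.05 only if F is significant at 0.05.

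| Case | Bonferroni | F-gated LSD | Ungated LSD |
|---|---|---|---|
| Neither drug works: any claim | 4.6% | 4.2% | 9.1% |
| Both 1.5%: per drug / at least one / both | 70.0 / 84.2 / 55.8% | 74.5 / 82.2 / 66.9% | 79.1 / 90.6 / 67.5% |
| One 1.5%, other inert: active drug found | 70.0% | 74.5% | 79.1% |
| 1.5% and 0.75%: stronger drug found | 69.9% | 68.3% | 79.1% |
| Both 1.0%: per drug / at least one / both | 34.5 / 49.7 / 19.4% | 37.1 / 46.1 / 28.2% | 45.5% per drug |

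With both drugs at 1.5%, the verdict on at least one drug differs between ungated LSD and Bonferroni in 17.1% of trials, and between gated LSD and Bonferroni in 13.7%.

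**5. If 3% is a single-visit SD.** The SD of the change is 3√(2(1 − r)). The correlation r is not in the documents, so a range is shown.

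| r | SD of change | Power at 1.5%, alpha 0.05 | Power at 1.5%, alpha 0.025 |
|---|---|---|---|
| 0.3 | 3.55 | 65% | 54% |
| 0.5 | 3.00 | 79% | 70% |
| 0.7 | 2.32 | 95% | 91% |

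An SD of change of 2.69 corresponds to r = 1 − 2.69²/18 = 0.60.

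**The case against.** The best defence is that a natural reading removes the conflict. Placing LSD within the ANOVA may mean the gated form, which controls family-wise error with three groups (4.2% in step 4). The Bonferroni sentence may be aimed at multiple end points. Both readings are possible, but the text states neither, and gated LSD and Bonferroni still disagree on at least one drug in about 14% of trials when both drugs give 1.5%.

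Second, the plan names the ANOVA first, and Purpose and Objectives treats the drugs as alternatives. Finding at least one effective drug is therefore a fair definition of success. On that definition, with both drugs at 1.5%, power exceeds 80% under Bonferroni (84%) and gated LSD (82%). This stands, and it limits the point. It does not cover the case where only one drug works (70% and 75% for the active drug).

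Third, the plan calls its SD conservative. If the SD of the change is about 2.69 or less, Bonferroni reaches 80% per drug at 1.5%. That is possible, but the documents give no figure to support it and concede that data on change are limited.

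A reader might also infer that 62 per group was miscalculated. It was not: it is right for 1.5% at uncorrected alpha.

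**Conclusion.** The point holds for per-drug power, for finding both drugs, and for the case where only one drug works. With 62 evaluable per group and an SD of change of 3%, applying Bonferroni to the two contrasts gives about 70% power per drug at 1.5% and 56% for both drugs. Leaving LSD ungated gives about 9% family-wise error. As written, the section neither selects a rule nor matches the stated power of 0.8 to a rule that controls the error.

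Two stronger readings are tempting. One is that the trial is underpowered on every definition of success; the 84% and 82% for at least one drug contradict that. The other is that the plan commits to an uncontrolled error rate; it does not, because a gated or Bonferroni reading remains open.

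The unstated design difference and the unstated meaning of the SD are clarifications that would not make a finding alone. They matter here because every power figure depends on them. This should be fixed, and the repair is a matter of wording.

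**What to change.** Keep enrolment unchanged. Before strain results by group are seen, revise the Sample Size and Data Analysis text as follows.

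1. **Replace the pairwise LSD sentence with one rule, and limit the general Bonferroni sentence to match.**
   - *Option A:* each drug is compared with usual care at two-sided alpha 0.025 (Bonferroni, two comparisons). Delete the LSD wording.
   - *Option B:* each drug is compared with usual care by LSD at two-sided alpha 0.05 only if the three-group F-test is significant at 0.05. State that the Bonferroni sentence does not apply to these two tests.
2. **Cover the nonparametric route.** Name the pairwise test that follows Kruskal-Wallis and apply the same rule to it.
3. **Restate power for the chosen rule only,** with 62 evaluable per group, design difference 1.5% and assumed SD of change 3%. With both drugs at 1.5% (per drug / at least one / both), A gives about 70 / 84 / 56% and B about 75 / 82 / 67%. Per-drug power with both drugs at 1.0% is about 34-35% for A and 37% for B. If 3% is a single-visit SD, restate these with the assumed correlation.

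The sponsor should choose, since neither option is better throughout. B finds an active drug more often when the effects are equal or one drug is inert. A finds the stronger drug slightly more often (70% against 68%) when the other has half the effect, but finds the weaker one less often (about 20% against 27%).

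**Cost.** No extra patients. Stated per-drug power falls below 80%, and some pairwise p-values under 0.05 no longer count. Under A these are p-values between 0.025 and 0.05, about 9% of trials per drug at a true 1.5% (79.1% − 70.0%). Under B they are those without a significant F-test. With both drugs at 1.5%, B loses every positive claim in about 8% of trials (90.6% − 82.2%).
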